# **3.0 Study Population**

Sixty HIV-uninfected, sexually active women — 30 at low risk for HIV infection and 30 at higher risk for HIV infection — from Pune, India, will be enrolled in this study. In addition, the single male sexual partner of female participants will be asked to provide informed consent for the study and will be invited to take part in study focus groups. Participants will be selected for this study according to the criteria in Sections 3.1 and 3.2. They will be recruited as described in Section 3.3. Conditions for withdrawal from the study are described in Section 3.4

# 3.1 Inclusion Criteria

# 3.1.1 All Female Participants

Women who meet all of the following criteria (by self-report, unless otherwise specified) are eligible for inclusion in this study:

- Age 18-45 years.
- Able and willing to provide written informed consent to take part in the study.
- HIV-uninfected by licensed enzyme immunoassay (EIA).
- Have a regular menstrual cycle with a minimum of 21 days between menses, or are amenorrheic due to long-acting progestin use.
- Have had no change in hormonal contraceptive use in the three months prior to screening and agree to continue use of their preferred contraceptive method while in the study, provided these methods are not listed below as exclusionary methods.
- Have a normal Pap smear at screening, or are able to document a normal Pap smear within three months prior to screening.
- Are sexually active with a single male sexual partner who is eligible for this study per Section 3.1.3 and 3.2.3 below.
- Agree to abstain from sexual intercourse beginning 48 hours prior to the Enrollment Visit.
- Able and willing to complete Daily Study Records.
- Agree for the duration of the study to:
  - > apply 0.5% PRO 2000/5 Gel (P) as required per protocol;
  - have vaginal intercourse only with the single male sexual partner who is eligible for this study per Section 3.1.3 and 3.2.3 below;
  - have vaginal intercourse at least two times per week while taking part in the study;
  - use study-provided condoms for each act of vaginal intercourse while taking part in the study;
  - > agree for the duration of the study to abstain from:
    - insertion of fingers and other objects into the vagina
    - receiving oral sex
    - receiving anal sex
    - using a female condom, diaphragm, or cervical cap
    - using any vaginal product other than 0.5% PRO 2000/5 Gel (P), including lubricants, desiccants, or feminine hygiene products
    - douching
    - participating in other vaginal microbicide or contraceptive studies while taking part in this study; and
    - using non-therapeutic intravenous drugs.

# 3.1.2 Female Participants at Higher Risk for HIV Infection

**In addition to** the criteria specified in Section 3.1.1, in order to be eligible for inclusion in the study as participants at **higher risk** for HIV infection, women must meet at least one the following criteria (based on participant knowledge and self-report):

- Have been diagnosed and/or treated for an STD (other than HIV) during the three months prior to screening.
- Have a current male sexual partner who was diagnosed or treated for an STD (other than HIV) in the three months prior to screening.

Note: Potential participants who are diagnosed with an STD at the time of study screening will be treated for the STD. Participants will be encouraged to refer their male partners for diagnosis and treatment, however partner notification will not be undertaken. Re-screening will be offered to participants after both partners complete treatment, if applicable.

# 3.1.3 Inclusion Criteria for Male Partners of Female Participants

Male sexual partners of female study participants who meet all of the following criteria (by self-report, unless otherwise specified) are eligible for inclusion in this study:

- Age 18 years or older.
- Able and willing to provide written informed consent, in person, to take part in the study.
- HIV-uninfected by licensed EIA.
- Free of STD symptoms at enrollment.
- Agree to abstain from sexual intercourse beginning 48 hours prior to the Enrollment Visit.
- Able and willing to have vaginal intercourse with their partner who is taking part in the study at least two times per week.
- Agree for the duration of the study (14 days) to:
  - > have vaginal intercourse only with the female study participant;
  - have vaginal intercourse with the female study participant at the usual frequency of at least two episodes per week;
  - use study-provided male condoms for each act of vaginal intercourse.

Note: Male partners who report STD symptoms at the time of screening will be offered an exam and clinically appropriate STD work-up. Those who are diagnosed with an STD will be treated, as will their female partners, based on the findings of their own screening and enrollment work-ups. Both the female participant and the male partner will be eligible for re-screening after treatment is completed. If the male partner refuses treatment of an STD, the female partner will not be eligible for participation in the study.
Since each partner will be screened and given his/her test results, no partner notification is required.

#### 3.2 Exclusion Criteria

#### **3.2.1** All Female Participants

Women who meet any of the following criteria by self-report at screening or enrollment, unless otherwise specified, will be excluded from this study:

Note: Women with observed abnormalities as described below will be referred for appropriate clinical follow-up and/or treatment. Since all potential participants are eligible for India's national health service, further clinical care will be provided at no cost to the participant.

- Are menopausal.
- Are currently breastfeeding.
- Are currently using, or within the year prior to screening have used, non-therapeutic intravenous drugs.
- Are pregnant (based on a urine pregnancy test).
- Have one or more grade 3 or higher liver, renal, or hematology abnormalities, as defined by the Division of AIDS (DAIDS) Toxicity Tables at screening.
- Have a positive urine culture.
- Have a clinically detectable genital abnormality (i.e., vulvar, vaginal, cervical and/or perianal ulcer and/or lesion).
- Have a history of adverse reaction to anticoagulant(s).
- Have a history of sensitivity/allergy to latex.
- Have used any spermicide or spermicidally lubricated condom within the past week (prior to enrollment).
- Have participated in any other investigational drug trial within 30 days prior to screening .
- In the three months prior to screening have (any of the following):
  - used an intrauterine contraceptive device,
  - ▹ had an abnormal Pap smear,
  - ▹ been pregnant,
  - ➢ had gynecologic surgery,
  - ➢ had breakthrough menstrual bleeding, or
  - ➤ had vaginal bleeding during or following sexual intercourse.

#### 3.2.2 Female Participants at Low Risk for HIV Infection

**In addition to** the exclusion criteria specified in Section 3.2.1, women will be excluded from the study as **low risk** participants if they meet any of the following criteria (based on participant knowledge and self-report):

- Have been diagnosed and/or treated for an STD (other than HIV) or pelvic inflammatory disease in the three months prior to screening.
- Have a current male sexual partner who was diagnosed or treated for an STD (other than HIV) in the three months prior to screening.
- Have a current male sexual partner who has injected non-therapeutic drugs in the three months prior to screening.
- Have signs, as seen on pelvic exam, consistent with an STD, other genital tract infection other than bacterial vaginosis (BV) or trauma, including:
  - ➤ vaginitis,
  - ➢ cervicitis,
  - ➢ edema,
  - ➢ erythema,
  - ➢ ecchymosis,
  - petechial hemorrhage,
  - > vulvar or cervicovaginal lesions, ulcers, or abrasions,
  - subepithelial hemorrhage and swelling, and
  - laboratory findings indicative of genital tract infection other than asymptomatic BV.

Note: Signs of asymptomatic BV include the presence of white to grey homogeneous discharge, positive whiff test (amine odor) with addition of KOH, pH>4.5, presence of clue cells, decrease in lactobacilli morphotypes, and increase in non-lactobacilli morphotypes. Women with clinical or gram stain evidence of BV and symptoms (discharge, odor, itching )at screening should be treated and re-evaluated for inclusion as low risk participants. Women without symptoms, but with clinical or gram stain evidence of BV, or asymptomatic yeast colonization, are eligible as low risk participants.

#### **3.2.3 Male Participants**

Men who meet any of the following criteria by self-report at screening or enrollment will be excluded from this study:

- Have history of adverse reaction to latex
- Refuse examination and/or treatment for an STD or STD symptoms

#### 3.3 Participant Recruitment

The study will be conducted at Jehangir Hospital and Medical Center. However study participants will be recruited from three other clinical settings affiliated with the HIV Prevention Trials Unit in Pune, India. Specifically, the National AIDS Research Institute (NARI) has established clinical settings to collaborate with the HPTN, as follows:

- the RTI Clinic attached to the Gynecology Outpatient Department of the Sassoon Hospital, attended by female gynecology patients;
- the Skin and Venereal Disease Departments of the Sassoon Hospital, attended by male and female STD patients;
- the Gadikhana Clinic, attended primarily by male and female STD patients.

# Note: The Sassoon Hospital is a large referral hospital with an extensive catchment area affiliated with the BJ Medical College.

Men and women attending any of the above clinics routinely are offered HIV and STD screening. Those who provide written informed consent for screening are tested, and those who test positive for treatable STDs are provided treatment according to the US Centers for Disease Control and Prevention (CDC) guidelines. To date, HIV-uninfected persons have been offered enrollment in a long-term follow-up study of HIV incidence. When HPTN 047 opens, HIV-uninfected women also will be invited to screen for this study (co-enrollment in the long-term follow-up study will not be precluded). Low risk participants will be recruited primarily from the RTI Clinic, however eligible low and higher risk participants will be accepted from all locations. For higher risk participants, in addition to direct outreach to female participants, HIV-uninfected males diagnosed with an STD will be informed of the study and invited to refer their female partners for screening.

Although it is expected that recruitment from the three locations listed above will fulfill the study enrollment goals in a timely manner, additional capacity also may be provided through collaboration and recruitment at three other clinics that NARI operates in Pune. Patients are referred to these clinics from all over Pune as well as from other nearby cities.

#### 3.4 Participant Withdrawal

Once a participant has enrolled in the study, the study site will make every reasonable effort to retain her for the 14-day study follow-up period. Given the relatively small study sample size, and the importance of ascertaining all safety outcomes among study participants, 100 percent retention of enrolled participants is targeted. Study site staff are responsible for developing and implementing local standard operating procedures to achieve complete follow-up.

However, participants may withdraw from the study for any reason at any time. The Investigator also may withdraw participants from the study in order to protect their safety and/or if they are unwilling or unable to comply with required study procedures. Participants also may be withdrawn if the study sponsor or US or Indian regulatory authorities terminate the study prior to its planned end date.

Every reasonable effort will be made to complete a final evaluation of participants who terminate from the study prior to Day 14, and study staff will record the reason(s) for all withdrawals from the study in participants' study records.

### 4.0 Study Product Considerations

### 4.1 Drug Substance

PRO 2000/5 is a polyanionic polymer consisting of alternating 2-naphthalene sulfonic acid sodium salt and methylene units. The weight-average molecular weight ( $M_w$ ) is 5±1 kD and the polydispersity ( $M_w/M_n$ ), a measure of molecular weight distribution, is low (1.2). PRO 2000/5 is synthesized by the acid catalyzed condensation of 2-naphthalene sulfonic acid with formaldehyde, followed by neutralization and molecular weight fractionation.

# 4.2 Product Preparation and Labeling

PRO 2000/5 Gel (P), 0.5% is a clear, pale yellow aqueous gel formulation containing 0.5% (w/w) PRO 2000/5, Carbomer 1382, lactic acid, trolamine and a combination of common preservatives (methylparaben, propylparaben, and sodium benzoate). It is buffered to pH 4.5. The human dose is 2 g (approximately 2 mL). PRO 2000/5 Gel (P), 0.5% is packaged in single dose, lacquer-lined, aluminum tubes.

Supplies of 0.5% PRO 2000/5 Gel (P) will be provided to study participants in boxes containing 16 tubes and 16 single-use vaginal applicators each. The clinical material is prepared under Good Manufacturing Practice (GMP) conditions for Indevus Pharmaceuticals, Inc. by Dow Pharmaceutical Sciences, Inc. Petaluma, CA, USA. Product will be shipped to the site by the DAIDS Clinical Research Products Management Center (CRPMC).

Supplies of 0.5% PRO 2000/5 Gel (P) are to be stored below  $35^{\circ}$  C in a secure area. Participants will be instructed to store the product at room temperature. The product has been shown to be stable for 6 months at  $40^{\circ}$  C/75 percent relative humidity.

The label on each kit will contain the following information:

The label on each tube will contain the following information:

#### 4.3 Dose Regimen

Study participants will be instructed to insert one dose (2 g) of PRO 2000/5 Gel (P) twice daily for 14 consecutive days, beginning on Day 0, the day of the study Enrollment Visit. Participants will be further instructed that, (a) on days when they do not have sexual intercourse, the gel should be applied once in the morning and once in the evening, and (b) on days when they have sexual intercourse, whenever possible, gel application should be timed to coincide (up to one hour before) with intercourse. However, if more than two episodes of intercourse occur on a single day, only two doses should be used. Detailed instructions and practical examples will be provided to study participants at enrollment.

Participants also will be instructed to engage in vaginal intercourse at least twice per week while taking part in the study, preferably within one hour after application of the gel. Study staff will review instructions for dispensing, administering, and storing PRO 2000/5 Gel (P) with each participant at her Enrollment Visit. Written instructions will be provided to each participant. Instruction will include a demonstration of the proper insertion technique using a pelvic model. In addition, participants will be given the option of inserting their first dose of the product while at the study site, under the supervision of the study clinician.

Assuming adherence to the dosing regimen, administration of doses 1-14 will take place on study Days 0-6. The fifteenth dose will be administered after the Day 7 Follow-up Visit — such that the dose does not interfere with the pelvic exam scheduled to take place on Day 7 — and the last dose will be administered on Day 13 (i.e., the day before the Day 14 Follow-up Visit).

#### 4.4 **Product Accountability**

The site pharmacist will maintain an accurate inventory and accountability record of study products received and subsequently dispensed. After the study is completed (or otherwise terminated), all unused study product must be returned to Indevus Pharmaceuticals, Inc., or destroyed at the site, in accordance with instructions from Indevus Pharmaceuticals, Inc.

#### 4.5 Adherence Assessment

Participants will record on their Daily Study Records the date and time of each product administration. The records also will collect information on the timing of sexual activity and the emergence/resolution of any symptoms experienced. The investigator or designee will review the Daily Study Records with each participant at her Day 2, Day 7, and Day 14 Follow-up Visits to assess adherence to the study product use and sexual activity requirements.

Twice daily administration of PRO 2000/5 Gel (P) on 14 consecutive study days, beginning with Day 0 is targeted, however lapses of consecutive day use will be accommodated, as follows:

• Participants who miss one or both doses on one day out of 14 will be instructed to complete two applications on one additional day (as soon as possible after Day 13) to achieve a total of 14 days of exposure prior to onset of the next menstrual period.

• Participants who miss one or both doses on two days out of 14 will be instructed to complete two applications on two additional days (as soon as possible after Day 13) to achieve a total of 14 days of exposure prior to onset of the next menstrual period.

Participants who complete twice daily administration of PRO 2000/5 Gel (P) on each study day between the Enrollment Visit (inclusive) and the Day 14 Followup Visit, as well as participants who adhere to one of the scenarios described above, will be considered adherent to the product use regimen. In addition, participants who experience an adverse event (AE) that requires product discontinuation (see Appendix III), but complete twice daily administration on the days preceding the AE will be considered "adherent." Participants who have fewer than two episodes of vaginal intercourse between study Days 0 and 6 will be encouraged to have at least two episodes between Days 7 and 13. Such participants will not routinely be withdrawn from the study, provided they are willing to try to become compliant for the remainder of the study.

Non-adherent participants (i.e., those who miss one or both doses on three or more days out of 14 in the absence of an AE that requires product discontinuation) will be encouraged to complete twice daily product use on as many days as possible during the 14-day product use period, and will not be replaced. These participants will be asked their reasons for non-adherence, and this information will be recorded on study case report forms.

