Four women discontinued product use because of (1) HSV cervicitis, (2) inappropriate enrollment (pregnancy), (3) urinary tract infection, and (4) vulvovaginal erythema and cervicovaginal abrasions. In the course of the study, 73 percent of the women reported adverse events that could have been product-related, with 60 percent of the women reporting only mild events and 13 percent reporting moderate events. Colposcopy was abnormal in 38 percent of the subjects, with abrasion (16 percent), erythema (16 percent), or ulceration (11 percent) being most common findings. These findings were usually mild and resolved during or shortly after discontinuation of product use. Half of the epithelial disruption findings were linked to possible applicator or speculum trauma, sexual activity, or HSV infection; all ulceration findings occurred in the twice daily frequency groups.

Other common, but transient, adverse events included vaginal discharge (27 percent) or bleeding (25 percent), which was usually spotting that stopped while product use continued, burning (16 percent), or irritation (14 percent). One participant showed clinically silent elevations in bilirubin and liver function test values, but no other clinically significant changes in laboratory safety parameters were observed. Differences in PRO 2000/5 concentration, frequency of use, or HIV status, did not appear to be associated with differences in the prevalence of adverse events. Overall, PRO 2000/5 Gel (P) at concentrations up to 4% administered twice daily was judged to be safe and well tolerated in the two study populations.

In a Phase I penile safety study, HIV-uninfected men applied either 4% PRO 2000/5 Gel (P) (n=24) or a gel containing the inactive ingredients of PRO 2000/5 Gel (P) (n=12) to the penis for seven consecutive days. About one in six users of both gels reported mild transient symptoms of genital itching, tingling, irritation, or abrasion. Additional users of both gels reported dryness or flaking of the dried gel. Preliminary findings from a similar Phase I clinical trial in HIV-1 seropositive men were comparable. PRO 2000/5 Gel (P) is not expected to have significant adverse effects on the partners of study participants, should they be exposed to the gels while having sexual intercourse with participants in the absence of a condom.

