# Appendix III. Outcomes, Diagnostics, and Follow-Up Procedures

## **Appendix III. (Continued)**

Vaginitis (findings on exam such as vaginal discharge)	Temporarily discontinue except for asymptomatic candida vaginitis	Perform wet mount for candida vaginitis , trichomoniasis , and bacterial vaginosis.	If laboratory results confirm pathogen, recruit an additional participant.	See below
Bleeding/Spotting	Temporarily discontinue (until evaluated)	Naked eye evaluation and/or colposcopy		If determined to be endometrial bleeding with no other source, continue product use. Re-evaluate in 72 hours if the participant reports the bleeding/spotting has not resolved.
Suspected cervicitis (findings on exam such as discharge from cervical os)	Provisionally continue	Evaluate for N. gonorrhoeae and C. trachomatis.	If laboratory results confirm pathogen, discontinue treatment and recruit an additional participant.	Treat with oral medication and re- evaluate in 48-72 hours. If condition is worse, discontinue product use.
Petechial hemorrhage	Continue	Naked eye evaluation and/or colposcopy		Re-evaluate by speculum examination in 48 to 72 hours. If the condition is significantly worse, discontinue product use. Otherwise, continue product use.
Ecchymosis	Continue	Naked eye evaluation and/or colposcopy		Re-evaluate by speculum examination in 48 to 72 hours. If the condition is significantly worse, discontinue product use. Otherwise, continue product use.

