#### Vaginitis:

- For trichomonas or symptomatic BV, treat or refer for treatment. Do not resume product use.
- For symptomatic Candida vaginitis: manage with oral medication and re-evaluate in 3-5 days. If resolved, restart product use. If observed at Day 14, treat and follow up to document resolution.
- For asymptomatic Candida vaginitis :
  - If a participant has asymptomatic Candida vaginitis at the Day 7 Visit she should continue product use and be re-evaluated at the Day 14 Visit
  - If at the Day 14 Visit there are signs and symptoms compatible with vaginitis, treat and follow-up to document resolution.

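### Section 4.5 scores adherence only up to the AE, so a woman held under Appendix III and cleared to restart is adherent however she doses afterwards

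*Protocol*

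**What the plan says.** Section 4.5 gives three routes to being classed as adherent. The first is full twice-daily use. The second is a make-up route for one or two missed days; for two days it reads "Participants who miss one or both doses on two days out of 14 will be instructed to complete two applications on two additional days". The third is for women whose AE requires product discontinuation, with a reference to Appendix III: those who have such an AE "but complete twice daily administration on the days preceding the AE will be considered 'adherent". The non-adherent are "those who miss one or both doses on three or more days out of 14 in the absence of an AE that requires product discontinuation".

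The third route sends the reader to Appendix III, which contains both stops and holds. Trichomonas and symptomatic BV are stops without resumption. Other entries lead back to product:

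- The vaginitis row reads "Temporarily discontinue except for asymptomatic candida vaginitis". For symptomatic Candida the note below the table says "manage with oral medication and re-evaluate in 3-5 days. If resolved, restart product use".
- The bleeding/spotting row reads "Temporarily discontinue (until evaluated)". Use continues if the bleeding is found to be endometrial with no other source.

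Section 4.6 recognises only continuation and discontinuation. Neither 4.5 nor 4.6 says how held days, or days after a restart, are scored.

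The definition is used in two places. Section 7.1.2 makes the adherent proportion, as defined in 4.5, the first secondary endpoint. Section 7.2 relies on an adherent subgroup when it calls the power robust to non-adherence.

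**The concern.** The AE route looks backwards only. That is reasonable for a woman who stops for good, because she has no later days on which to adhere. It does not suit a woman who is held, cleared and told to resume: her later days are real opportunities to use or miss the gel, and the rule ignores them.

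Two things are at stake. The adherence endpoint could count as a success a woman who declined the product for most of the dosing period. The adherent subgroup, meant to show toxicity among women properly exposed, could include women with very little exposure. In addition, an analyst who took discontinuation to mean permanent discontinuation would classify some of the same women the opposite way and report a different rate from the same data.

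**Working it through.** **1. The plan's own figures.** Section 7.2 uses the exact binomial: Pr(2+) = 1 − (1−p)^n − n·p·(1−p)^(n−1).

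- n = 60, p = 0.07: 1 − 0.93^60 − 60 × 0.07 × 0.93^59 = 0.929 (stated .93).
- n = 60, p = 0.05: 0.808 (stated .81).
- 10% non-adherent, n = 54, p = 0.07: 0.899 (stated 90%).
- 20% non-adherent, n = 48, p = 0.08: 0.906 (stated 90%).

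All reproduce.

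**2. One woman under each reading.** Suppose that she doses fully on Days 0 and 1, is held from the Day 2 visit for symptomatic Candida, and is cleared on Day 6. The four-day hold is chosen from the 3-5 day range. Held days are 2 to 5; days after clearance are 6 to 13, which is 8 days.

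| Use after clearance | Hold counts as discontinuation | Only permanent stops count |
|---|---|---|
| All 8 days | Adherent | 4 missed days: non-adherent |
| None of 8 days | Adherent | 4 + 8 = 12 missed days: non-adherent |

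Neither reading separates the two rows. In the second row she has used 2 of 14 days, or 4 of 28 doses, and the first reading still calls her adherent.

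**3. Which holds matter on the second reading.** Days missed through a hold of h days starting on day d are min(h, 14 − d). A hold of 1 or 2 days never exceeds two missed days and can be made up after Day 13. A 3-day hold reaches three missed days if it starts on any of Days 0 to 11, which is 12 of 14 start days; so do 4- and 5-day holds. Short holds therefore do not by themselves cause non-adherence, although a 2-day hold uses up the whole allowance.

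**4. Size.** The documents give no count of women held and restarted, so k is an assumption. Suppose that k women are held for three or more days, resume fully, and all other women are adherent. The first reading gives 60/60. The second gives (60 − k)/60.

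| k (assumed) | Adherent, first reading | Adherent, second reading | Subgroup n, second reading | Pr(2+ events at 7%) |
|---|---|---|---|---|
| 3 | 100% | 57/60 = 95% | 57 | 0.92 |
| 6 | 100% | 54/60 = 90% | 54 | 0.90 |
| 12 | 100% | 48/60 = 80% | 48 | 0.86 |

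With all 60 women the probability is 0.93. Each woman shifts the endpoint by 1/60 = 1.7 points.

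**The case against.** Much of the case on the other side stands.

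*The second reading is weak.* Appendix III itself calls a hold a temporary discontinuation, 4.5 cross-refers to Appendix III, and 4.6 has no third category. A held woman is therefore literally within the AE exemption. A reader might infer that the protocol brands women non-adherent for obeying Appendix III, but that requires discontinuation to mean permanent discontinuation, which no section says. The second reading shows what an analyst might do, not what the text requires.

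*Bleeding cannot be used to size the problem.* A reader might take the bleeding rate in the earlier HPTN trial, compute 0.25 × 60 = 15 women, and conclude that adherence could be 45/60 = 75% with a subgroup probability of 0.83. Section 1.2.2 describes "bleeding (25 percent), which was usually spotting that stopped while product use continued", so the rate does not measure how often product was held, and it comes from 2% and 4% gel. The bleeding hold has no stated length, and holds of 1 or 2 days can be made up. Nor should a subgroup of 45, which is 25% non-adherence, be set against a claim made for 10%.

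*Low exposure among adherent women is partly intended.* Section 4.5 deliberately counts women who stop early for an AE. That is a choice, and it is not disputed here. It does not explain ignoring days after a woman has been cleared to restart.

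*Detail of this kind often goes into a SAP.* That would answer a missing derivation. Here Section 7.1.2 adopts the 4.5 definition as the endpoint, and that definition, applied as written, gives the wrong class.

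**Conclusion.** The point holds in a narrow form. On the literal text of 4.5, a woman discontinued temporarily under Appendix III and cleared to restart is adherent whatever she does afterwards, provided that she dosed fully before the AE. Symptomatic Candida vaginitis is the clearest case.

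The effect is confined to a descriptive secondary proportion, at 1.7 points per woman, and to membership of the adherent subgroup. The gap between readings is 5, 10 or 20 points for an assumed 3, 6 or 12 women, and it also assumes holds of at least three days and full adherence by everyone else. The primary tabulation in 7.4.1 includes all enrolled women and does not depend on adherence, and the figures in 7.2 stand. The severity is minor; the correction is worth making because it is cheap and the rule as written misclassifies.

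**What to change.** Reconcile Sections 4.5 and 4.6 and Appendix III on scoring only, leaving every hold, restart and dosing rule as it is:

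- Keep the endpoint as a proportion of participants.
- Confine the route based on days before the AE to women whose product use is not resumed.
- For women restarted under Appendix III, count held days as neither taken nor missed, and apply the existing threshold of three or more missed days to all other days, including those after clearance.
- Report doses used alongside any adherent-subgroup result.

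In the example above, the woman who uses product on all 8 days after clearance has 0 missed of 10 permitted days and is adherent. The woman who uses none has 8 missed of 10 and is not.

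The cost is a sentence or two in 4.5 and one derived variable. Hold and clearance dates must be captured or derived: the Daily Study Records hold application dates and times, but the protocol does not show that the forms record hold dates. Restarted women are judged on fewer than 14 days, and the threshold loses force for late restarts: a woman cleared on Day 12 has only Days 12 and 13 left and cannot reach three missed days on those alone. Showing doses used makes that visible.
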